## **B.** Discussion of Statistical Methods:

This study in adolescent patients is a randomized, parallel-group comparison of treatment with TMS as compared to a sham control. It will be conducted at approximately 16 sites in the United States and Canada, with independent randomization protocols within each site, using a permuted block design to improve balance within site. The primary outcome is the last post-treatment symptom score (LV) measured using the primary efficacy outcome measure (efficacy variable and point of declaration are blinded to the Investigator) for each subject. LV will come from the 6-week visit, unless the data is missing, in which case the last observation will be carried forward (LOCF). The analysis will be performed on the strict intention-to-treat sample of all evaluable subjects, meaning those subjects with a baseline and at least one post-baseline observation available for analysis.

Poorly recruiting sites, defined as those with fewer than 2 randomization blocks, will be pooled into one or more pseudo-sites for purposes of analysis. To ensure that nearly all sites will be of adequate size we will adopt a strict closure policy for sites that do not show early signs of enrollment success. With 16 sites, the average number of subjects per site is approximately 18, so there may be a few sites with fewer than 2 randomization blocks. A site that has not randomized at least 2 subjects in the first quarter of their enrollment may be closed. Then if as many as 2 sites are closed, and one poorly performing site eludes closure, there will be no more than one pseudo-site comprising a total of no more than 2 subjects from the closed site and approximately 11 from the poorly performing site, or no more than 13 subjects in all (i.e. <5% of the total sample).

As noted elsewhere in this protocol, the sites were blinded to the point of primary efficacy declaration in order to improve the study's signal detection ability. Point of declaration for the primary outcome measure is included in this document, which was not shared with any of the study sites.

The null hypothesis will be tested in an analysis of covariance of the LV (value from 6-week visit unless it is missing, then LOCF used), using baseline score, and ATR medication resistance level as fixed effect covariates, adjusting for site differences using a random effect. As discussed elsewhere, the ATR medication resistance levels will group subjects categorically by number of medications which have shown an adequate degree of resistance for that subject. These resistance levels will be grouped into two categories in statistical model, 0-1 in the current episode or 2-4 in the current episode, unless the final distribution of ATR scores in the study population suggests another allocation would be more statistically appropriate. All tests are two-sided, at the 5% level. The primary outcome should be available and meaningful for nearly all subjects, so the main analysis will be by strict intention-to-treat as defined above. An analysis of observed cases only will be performed as a secondary outcome measure. A site by treatment interaction analysis will be done as a secondary analysis to see if there is significant heterogeneity in the effect of TMS across sites. In particular, we will examine site-specific treatment effects (with confidence intervals) to test for evidence of true reversal of effect.

Secondary outcomes include other continuous measures, and within-subject dichotomous variables as outlined in the efficacy variables described elsewhere in this protocol. The treatment effect null hypothesis will be tested by logistic regression on treatment group assignment with adjustment for site and ATR medication resistance level. In addition, the longitudinal symptom scores will be analyzed with a general linear model adjusting for baseline scores and ATR medication resistance level, using a saturated means model for time since baseline, with treatment effect parameterized by a linear effect in time. The correlation of scores within individuals over time will be handled by allowing a within-subjects residual covariance matrix selected by exploration of the sample semi-variogram, as described by Diggle, Liang and Zeger. If this exploration reveals that a mixed model approach will fit the covariance structure better, random effects will be included in the model. As in the main analysis, site by treatment interactions will be tested.

In addition to testing the hypothesis noted above in the study alone, a meta-analysis will be used to establish evidence of efficacy. Specifically, in addition to the evidence to be obtained in this study protocol, there are 44-02219-204. Rev C 21-JAN-2019 Page 5 of 28

already two large, randomized, multisite sham-controlled studies of the use of the NeuroStar TMS Therapy® System in adult patients (ages 18-70 years of age) with major depressive disorder. These data are statistically important to consider in the interpretation of the data to be collected in the adolescent study population using the NeuroStar® TMS device. Therefore, a frequentist analysis will be used to demonstrate the effectiveness of the NeuroStar TMS Therapy System across ages 12-70 by borrowing data from the two adult studies to be used in a meta-analysis with the adolescent study data. This approach effectively allows meaningful computational use of the preponderance of adult study evidence with the adolescent study data to permit a "sample-sparing" adolescent study design. This approach is clinically justified by the substantial evidence of safety and effectiveness already shown in the adult patient population, the biological and clinical continuity of the disease state from adolescence to adulthood, the shared mechanism of action of transcranial magnetic stimulation across age groups, and because of the significant unmet need in treatment options available for adolescent patients with major depressive disorder.

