10.2 Efficacy and Safety Assessments

Phase I

See Appendix A for schedule of events.

Outcome Assessments

Trained physicians and raters will administer all diagnostic assessments and clinical interviews determining study eligibility during screening and prior to randomization. All study staff will be trained on study procedures by Neuronetics staff.

Outcome screening will occur after both the Informed Assent/Consent Document and the HIPAA Authorization are signed. Baseline assessments will occur prior to the first TMS treatment session. Outcome measures in Phase I will be assessed at the end of treatment weeks 4 and 6. The following outcome assessments will be completed: HAMD/MADRS structured interview, CDRS-R, CGI-S, and QIDS-A17-SR.

Safety Assessments

A physical and complete medical and psychiatric history will be obtained at the screening visit.

Page 26 of 61

Vital signs including height, weight, blood pressure and heart rate will be collected at the baseline visit and at week 6.

Laboratory determination will be measured at screening and include: Blood chemistry, hematology, urine drug screen, and urine pregnancy for female subjects.

Subjects will be evaluated clinically for adverse events at each visit. Serious adverse events (SAEs) will be recorded as they occur and reported to Neuronetics by the study site within one business day of notification.

Cognitive function assessments will be conducted at the baseline visit and at week 6. The following tests from the NIH Toolbox Cognition Battery are used for this study:

- Education
- Handedness
- Attention
 - o Flanker Inhibitory Control and Attention Test
- Episodic Memory
 - Picture Sequence Memory Test
 - Auditory Verbal Learning Test (Rey)
- Executive Function
 - Dimensional Change Card Sort Test
 - Flanker Inhibitory Control and Attention Test
- Language
 - Picture Vocabulary Test
 - Oral Reading Recognition Test
- Processing Speed
 - Pattern Comparison Processing Speed Test
- Memory
 - List Sorting Working Memory Test

The C-SSRS will be completed weekly during TMS treatment to assess worsening of illness and suicidality. The YMRS will be completed at baseline and will be repeated based on reported change in symptoms.

Air conduction thresholds will be assessed for both left and right ears at the baseline visit and at week 6.

Phase II

See Appendix B for schedule of events. The schedule of efficacy and safety measures for Phase II will be identical to that of Phase I.

Phase III

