Secondary outcomes include other continuous measures, and within-subject dichotomous variables as outlined in the efficacy variables described elsewhere in this protocol. The treatment effect null hypothesis will be tested by logistic regression on treatment group assignment with adjustment for site and ATR medication resistance level. In addition, the longitudinal symptom scores will be analyzed with a general linear model adjusting for baseline scores and ATR medication resistance level, using a saturated means model for time since baseline, with treatment effect parameterized by a linear effect in time. The correlation of scores within individuals over time will be handled by allowing a within-subjects residual covariance matrix selected by exploration of the sample semi-variogram, as described by Diggle, Liang and Zeger. If this exploration reveals that a mixed model approach will fit the covariance structure better, random effects will be included in the model. As in the main analysis, site by treatment interactions will be tested.

In addition to testing the hypothesis noted above in the study alone, a meta-analysis will be used to establish evidence of efficacy. Specifically, in addition to the evidence to be obtained in this study protocol, there are already two large, randomized, multisite sham-controlled studies of the use of the NeuroStar TMS Therapy[®] System in adult patients (ages 18-70 years of age) with major depressive disorder. These data are statistically important to consider in the interpretation of the data to be collected in the adolescent study population using the NeuroStar[®] TMS device. Therefore, a frequentist analysis will be used to demonstrate the effectiveness of the NeuroStar TMS Therapy System across ages 12-70 by borrowing data from the two adult studies to be used in a meta-analysis with the adolescent study data. This approach effectively allows meaningful computational use of the preponderamce of adult study evidence with the adolescent study datato permit a "sample-sparing" adolescent study design. This approach is clinically justified by the substantial evidence of safety and effectiveness already shown in the adult patient population, the biological and clinical continuity of the disease state from adolescence to

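### The secondary longitudinal model makes treatment linear in time and picks its covariance from a semi-variogram, but the acute phase has two post-baseline visits; on the natural reading week 4 is tied to about two-thirds of week 6

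*SAP*

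**What the plan says.** SAP Section 2.B, in the paragraph on secondary outcomes, states that "the longitudinal symptom scores will be analyzed with a general linear model adjusting for baseline scores and ATR medication resistance level". The time means are saturated, and treatment is handled differently: "using a saturated means model for time since baseline, with treatment effect parameterized by a linear effect in time". Protocol Section 15.2 has the same specification ("with treatment effect parameterized by a linear effect in time"). Neither document says whether a treatment intercept accompanies the slope.

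The within-subject correlation is to be handled through "a within-subjects residual covariance matrix selected by exploration of the sample semi-variogram". There is a fallback: "If this exploration reveals that a mixed model approach will fit the covariance structure better, random effects will be included in the model".

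On timing, Protocol Section 10.2 says: "Outcome measures in Phase I will be assessed at the end of treatment weeks 4 and 6". The Phase I schedule (Protocol Appendix A, reproduced in SAP Section 3.B) also marks the efficacy scales at taper week 3. Note m limits the taper to subjects who leave the study or move straight on to Phase III, and SAP Section 3.A.1 counts the taper within a nine-week Phase I. The SAP does not say whether the longitudinal model uses that assessment.

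**The concern.** Baseline is a covariate, so the response in this model is post-baseline only: two values per subject in the acute phase. A single slope in time since baseline then summarises two treatment contrasts with one number. The ratio between the contrasts comes from the model and not from the data. If the true effect levels off by week 4, or arrives mainly after it, the fitted effects at both visits are pulled away from the truth.

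The covariance step has a separate difficulty. A semi-variogram shows how dependence changes with the gap between measurements, and two visits supply only one gap.

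What is at stake is interpretation. The primary analysis carries the last value forward when week 6 is missing. This is the only repeated-measures model in the plan. If it disagreed with the primary result, a reader could not tell whether the carried-forward values or the linear constraint was responsible.

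**Working it through.** The plan states no figure for this model, so there is nothing to reproduce. The check has four steps.

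**Inputs.** Visits at weeks 4 and 6 (Protocol Section 10.2). Form of the treatment effect and role of baseline (SAP Section 2.B). The correlation r between weeks 4 and 6 and the variances are not given. I assume equal variances and r from 0.5 to 0.8, with 0.3 as a low value. The true effects are illustrative.

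**1. The ratio.** With effect(t) = b·t, effect(4)/effect(6) = 4/6 = 0.667. In schedule days it is 26/42 = 0.62 to 26/40 = 0.65. This follows from linearity through zero at baseline, not from the number of visits. With a treatment intercept the design rows are (1, 4) and (1, 6). The determinant is 6 − 4 = 2, so the rank is 2, both contrasts are fitted exactly and no ratio is imposed.

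**2. What one slope reports.** Generalised least squares gives b = t′V⁻¹d / t′V⁻¹t with t = (4, 6). With equal variances and true effects d4 and d6:

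fitted week 6 = 6·[(4 − 6r)·d4 + (6 − 4r)·d6] / (52 − 48r), and fitted week 4 = 4/6 of that.

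For example, at r = 0.5 with effects 3 and 3: 6·(1·3 + 4·3)/28 = 90/28 = 3.21, and week 4 is 2.14.

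| r | True 3.0, 3.0: fitted week 4, week 6 | True 1.0, 3.0: fitted week 4, week 6 |
|---|---|---|
| 0.5 | 2.14, 3.21 | 1.86, 2.79 |
| 0.6 | 2.07, 3.10 | 1.93, 2.90 |
| 0.7 | 1.96, 2.93 | 2.04, 3.07 |
| 0.8 | 1.76, 2.65 | 2.24, 3.35 |

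Week 4 is understated by 0.9 to 1.2 points in the plateau case and roughly doubled in the late-onset case. Week 6 is off by at most about 0.35/3.0 = 12% in these two cases. The weight on d4, 4 − 6r, turns negative when r exceeds 2/3. Above that value, a larger week-4 benefit lowers the fitted week-6 effect.

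**3. The covariance.** Weeks 4 and 6 give one lag, 6 − 4 = 2 weeks. One point on a semi-variogram cannot separate one serial-correlation shape from another. The full matrix has two variances and one covariance, three parameters in all. A random intercept and slope with residual error needs four (two variances, their covariance and the residual), more than two visits can identify. Adding taper week 3 (about week 9) gives lags of 2, 3 and 5 weeks, but only in the subjects who taper.

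**4. The price of removing the constraint.** The slope model's week-6 variance relative to the unconstrained variance is 36(1 − r²)/(52 − 48r): 0.871 at r = 0.3, 0.964 at 0.5, 0.993 at 0.6, 0.998 at 0.7 and 0.953 at 0.8. Freeing the effect multiplies the week-6 standard error by 1/√0.953 = 1.024 at worst for r from 0.5 to 0.8, and by 1/√0.871 = 1.07 at r = 0.3.

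**The case against.** The strongest reply is that linear growth from zero at randomisation is a legitimate pre-specified working model. If treatment has no effect at either visit the slope is zero, so the linear form does not bias the one-degree-of-freedom test. That stands.

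The reply can add that nothing important depends on the model. It is absent from the prioritised outcomes (SAP Table 6, Protocol Table 4) and from the success criteria in SAP Section 2.D. SAP Section 2.B also plans an observed-case analysis, and SAP Section 3.E allows an imputation sensitivity analysis if deemed necessary. That stands too.

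The week-6 error is also modest. Protocol Section 8.1 gives a 95% CI of −4.30 to 0.08 for the HAMD24 difference in the NIMH-funded adult trial (N=197), so a standard error of 4.38/3.92 = 1.12. If the variance is similar, N=100 gives 1.12·√1.97 ≈ 1.6, and 0.35 points is under a quarter of that.

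A reader might infer that the two-thirds ratio is certain. The documents do not support that, because they do not rule out a treatment intercept. A reader might also infer that the trial will publish a wrong week-4 effect. No section says that this model will report visit-specific effects, and SAP Section 3.E refers separately to week-4 and week-6 analyses with their own inclusion rules.

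What the reply does not rescue is the specification. On one reading it is constrained for no stated reason; on the other its central word has no content. The covariance step is uninformative on both, although no wrong result has been shown to follow from it.

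**Conclusion.** The longitudinal model as written does not fit the trial's visit schedule and is under-specified. This holds whichever reading is meant. The two-thirds constraint is conditional on a single slope through zero at baseline.

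Under that reading, for the two illustrative patterns and r from 0.5 to 0.8, fitted effects are 1.8 to 2.2 at week 4 against true values of 3.0 or 1.0, and 2.65 to 3.35 at week 6 against 3.0. These sizes rest on assumed correlations, equal variances and chosen effect patterns, none of which the documents give. A more extreme pattern gives a larger error: with no week-4 effect at all and r from 0.3 to 0.8, the fitted week-6 effect runs from 0.77 to 1.24 times the truth.

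It would be wrong to conclude that the efficacy claim is compromised. The primary ANCOVA of the week-6 or carried-forward value and the success criteria do not use this model. The point is a cheap improvement to a secondary analysis.

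**What to change.** In SAP Section 2.B, and in the matching text of Protocol Section 15.2, replace the longitudinal model with a mixed model for repeated measures on weeks 4 and 6. Include visit, treatment, treatment-by-visit, baseline score, ATR level, random site and an unstructured 2x2 within-subject covariance. Report the week-6 treatment contrast, with week 4 as supportive. State that the taper week-3 assessment is excluded, since who attends it depends on outcome. Delete the semi-variogram step and the random-effects alternative that depends on it.

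The cost is a change of wording and one extra mean parameter. The week-6 standard error rises by about 2.4% at most for correlations of 0.5 to 0.8, and by about 7% at 0.3. No additional data are needed.

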#### **D.** Flow of Analysis:

First, the adolescent study data will be analyzed standing alone. If the results of the analysis of the adolescent study shows a statistically significant treatment group difference in favor of the active treatment at a pre-specified alpha level = 0.05, then this study alone will be sufficient to establish efficacy in the adolescent population. If the stand alone analysis does not have statistically significant results, the meta-analysis will be performed.

Based on this meta-analysis, there are 3 essential criteria to declare success and conclude that the evidence rejects the null hypothesis of no difference between active TMS and sham TMS in adolescent patients with treatment resistant major depressive disorder. These criteria are:

- 1) The main effect of treatment on the primary efficacy variable of mean change from baseline on the HAMD24 in the adolescent/adult studies meta-analysis will be statistically significant, and fall below the specified alpha level of 0.05,
- 2) There will be no statistically significant evidence of interaction between Study and Treatment on the primary efficacy outcome variable at the pre-specified alpha level  $\geq 0.10$ ,
- 3) The study-specific treatment effect observed for the primary efficacy outcome variable in the adolescent study as a stand-alone analysis will reside between the ranges of 1.7 points to 5.5 points on the HAMD24, and to meet the maximum Type I error rate of 15%.

The criteria above are clinically justified based on the results using the HAMD24 outcome measure in the prior adult studies which ranges from 1.7 to 2.5 (O'Reardon, et al, 2007; George, et al, 2010). The maximum Type I error rate of 15% for the adolescent data alone is justified given the large dataset available in adults (N=491) and that adult and adolescent populations should respond similarly to TMS Therapy. Simulations using data from the adult studies and N=100 adolescents, shows that with a type I error rate of 5%, the observed HAMD24 mean difference between active and sham treatment would need to be 2.67, which would require a result greater than what it would need to achieve had it been considered alone. For this reason, the 15% type I error rate for the adolescent data is justified.

## Section 3. General Analysis Definitions

#### A. Study Phases:

The following are phase descriptions are included from the study protocol synopsis for the adolescent protocol. The phases/separate protocols are included in the protocols for the two adult programs.

### 1. Phase I (Randomized, Blinded):

For subjects randomized to the active treatment, stimulation will occur at a maximum of 120% magnetic field intensity relative to the subject's resting motor threshold (MT), at 10 pulses per second (10 Hz) for 4 seconds, with an intertrain interval of 26 seconds. Repositioning of coil, per NeuroStar User Manual, and prophylactic use of acetaminophen or ibuprofen will be allowed for subjects reporting sensations at or near the stimulation site which are uncomfortable. During the first week of treatment only, in the event that the subject cannot tolerate the treatment at these dose parameters, dose intensity may be titrated downward to 110% of the motor threshold, with all other dose parameters remaining the same. Treatment sessions will last for 37.5 minutes (75 trains) to provide a total of 3,000 pulses per treatment session. A maximum total of 36 treatments will be completed within 9 weeks of Phase I (including the 6 treatments administered during the 3-week taper phase). If the subject meets criteria (blinded to Site personnel) to enter Phase II, they will not complete the 3-week taper phase, resulting in a maximum total of 30 treatments.

## 2. Phase II (Non-Randomized, Open-label):

Subjects who do not achieve protocol-defined clinical benefit to treatment in Phase I will be offered the opportunity to undergo acute TMS treatment using the known-active therapy coil in Phase II. A maximum total of 36 treatments will be completed within 9 weeks of Phase II (including the 6 treatments administered during the 3-week taper phase).

Therefore, subjects who are randomized to active treatment during Phase I and subsequently enroll into Phase II will receive up to a total of 66 active treatments using stated study parameters within the 15-week combined timeframe (including one taper phase).

Subjects who are randomized to sham treatment during Phase I and subsequently enroll in Phase II will receive up to a total of 36 active treatments using stated study parameters within the 15-week combined timeframe (including one taper phase).

